14.3 Care escalation procedures

If the participant is in therapy, Inspire will hold responsibility and clinical governance accountability for the participant's mental health and wellbeing, including their own safety and where relevant the safety of others and including the safeguarding of children and vulnerable adults. If at point of referral or during the course of treatment, Inspire therapists become concerned about the welfare of any participant or immediate family member they will escalate their concerns through Inspire's standardised risk assessment, escalation, management and safeguarding policies and procedures. Where necessary they will contact the participant's GP to mobilise referral to crisis response, NHS primary or secondary care. Likewise, if a safeguarding and vulnerable adults concern is identified this will be escalated, acted on and reported to the relevant statutory body – safeguarding team.

Before the participant is referred to Inspire and after discharge, the participant's GP holds responsibility and accountability for the participant's mental health and wellbeing and this includes their safety. If the participant scores on the PCL-5 indicate an adverse event, the unmasked researcher responsible for participant safety will make contact with the participant within six hours of noting the rise in score and encourage them to contact their GP and/or case worker. They will advise the participant that they will need to contact the participants GP and/or case worker to alert them to the rise in PTSD symptoms. The research team will review all incoming follow-up PCL-5 and PHQ-9 scores within 72 hours of receipt.

All AE will be recorded and reported to the study PI within 72 hours and will be discussed at the biweekly research core-team sub-group meeting. A report will be included in the TSC reporting for review.

A Serious Adverse Event that occurs following discharge from Inspire but whilst in the trial will be investigated by one of the study's senior investigators (i.e. [name] or [name]) using Inspire's SAE investigational policies and procedures. The investigational report will be submitted to the DMEC chair.

The DMEC chair will be notified within 24 hours of the research team being notified of all serious adverse events.

All AE and SAE and the clinical and research team actions will be logged in the Trial Management File.

15 Ethics and regulatory approvals

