22.1 Appendix 1: Participant safeguarding protocol

The safety of potential and actual participants is the greatest ethical concern. Our feasibility safety protocol performed well and we have strengthened it to address the safety needs of ineligible participants and participants in the Waiting List (WL) arm of the study.

This Safety Protocol follows the best practice, professional guidelines, and local NHS policies for monitoring mental state and risk throughout the participants' involvement in the trial and will be facilitated by close liaison with clinical teams. The safety of the FIRST psychotherapy intervention will be monitored closely during therapy sessions and through regular contact with the participant's clinical team or GP.

The following comprises our safety protocol for all participants in the trial: those randomised to receive the Intervention immediately, those who are placed on the WL to receive FIRST in 20 weeks' time and those that withdraw. It addresses lines of responsibility and accountability, definitions relating to safety, escalation and safeguarding procedures in the event of notable clinical deterioration with or without an escalation in risk, alongside ensuring the safe and effective management of participants who are ineligible to enter the trial.

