1.0 Lines of responsibility and accountability

- 1.1 Up until the point at which a participant has undertaken their eligibility confirmation assessment with King's contracted Assistant Psychologists (AP) and before their details are forwarded to Inspire on randomisation and for therapy appointments to be allocated, the participant's GP holds responsibility and accountability for the participant's mental health and wellbeing and this includes their safety.
- 1.2 For those participants randomised to receive FIRST therapy immediately (the Intervention arm) from the point at which the participant's details are handed over to Inspire to arrange their therapy sessions through to the point of discharge, Inspire have responsibility and clinical governance accountability for the participant's mental health and wellbeing and including their own safety and where relevant the safety of others and including the safeguarding of children and vulnerable adults.
- 1.3 From the point of discharge from Inspire therapy to the point of 52-week follow-up or withdrawal from the trial, the Intervention participant's GP holds responsibility and accountability for the participant's mental health and wellbeing and this includes their safety.
- 1.4 For those participants randomised to receive FIRST therapy in 20 weeks (the Control arm) up until therapy begins the participant's GP continues to hold responsibility and accountability. At the point therapy delivery with Inspire begins at 20-weeks until the point of discharge approximately four weeks' later, Inspire have responsibility and clinical governance accountability. Once therapy is completed for these participants, they are discharged from Inspire and their time in the study is complete. Responsibility for the participant's mental health and wellbeing returns to their GP.
- 1.5 Participant safety will be a standing agenda item on every fortnightly core research team sub-group meeting.
- 1.6 Data Monitoring and Ethics Committee (DMEC) will meet once during the Proof of Concept trial and four times during the full trial and comprises two trauma experts and an independent statistician. The DMEC terms of reference will operate according to the King's Clinical Trials Unit Standard Operating Procedures. The research team will report any participant safety issues to the DMEC within 48 hours of each fortnightly core research team sub-group meeting.

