2.0 Definitions related of safety

- 2.1 Mental health safety symptom severity, deterioration is assessed using the PCL-5 selfreport screening questionnaire completed by the participant at the beginning of every therapy session until discharge. Any existing or emergent safeguarding and or vulnerable adult concern will be assessed and monitored at each session with proportionate action taken in accordance with legislative reporting requirements.
- 2.2 Mental health safety is assessed using the PCL-5 and PHQ-9 (question 9) self-report screening questionnaires completed by the participant at the following time points following FIRST therapy discharge (intervention arm), or while awaiting therapy commencement at 20-weeks (control arm): 6 weeks post randomisation, 12 weeks post randomisation, 20 weeks post randomisation and 52 weeks post randomisation (for those in the intervention arm).
 - 2.2.1 The named researcher will review all incoming follow up PCL-5 and PHQ-9 scores within 72 hrs of receipt.
 - 2.2.2 If PHQ9, Q.9 (risk of self-harm) is scored 1-3 this will trigger a safety contact email correspondence from the assessors (see 4.0).
- 2.3 PTSD Adverse Events are defined as a ≥10 point rise in the self-report PCL-5 since the previous therapy session or a 15 point rise from baseline or the maximum score of 80 being reached and/or relapse into alcohol and/or substance misuse at a hazardous level which integrated with the clinical judgement of the treating therapist will determine the action taken.
- 2.4 The risk of Self-Harm Adverse Event is defined as when the research team has been unable to make contact with the participant (see 4.5) on three separate occasions and contact is made from the research team to the participant's GP.
- 2.5 PTSD Serious Adverse Events are defined as hospital admission for mental ill-health, self-harm, suicide and attempted or completed suicide.

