3.0 Safety net procedures for between therapy and follow up time points

- 3.1 All participants will be offered a *Contact Card* at the point of randomisation. This will list the contact details of services to call 24/7 if they feel they need to talk with someone about their mental health outside of their therapy session and throughout their trial participation. Contact details will include Lifeline, Samaritans and their GP and where appropriate their Aftercare case worker and Inspire's 24/7 helpline.
 - 3.1.1 For participants in therapy, the therapist will record participant self-reports of all contacts being made in the therapy safety log.
 - 3.1.2 For participants in follow up, the researcher will note such self-reports in the data collected and ask the participant for details. Details, if provided, will be recorded in the researcher's participant safety log.
 - 3.1.3 The unblinded researcher will review the therapy database weekly to determine if any activity has been logged in the previous seven days.

4.0 Care escalation procedures in the event of a risk of self-harm reported on the PHQ-9

- 4.1 If the participant self-reports thoughts of self-harm on the PHQ-9, by answering 1-3 on question 9, the safety contact communication will be triggered.
- 4.2 On identifying a score of 1-3 on Q9, the research team assessor will contact the participant to ask them about their response and to suggest they may wish to speak to their GP for support.
- 4.3 If the research team assessor is unable to make contact or do not hear back from the participant within 24 hours, they will send a follow-up email.

- 4.4 If research team assessor still receive no response, they will send a third communication saying they have emailed the participant twice over the past two days and if they do not hear from them within 24 hours they will get in touch with their GP to let them know that they are concerned about them.
- 4.5 If this final communication does not elicit a response, the research team assessor will escalate the reporting and contact the GP, to voice our concerns. This will be reported to one of the study's senior investigators ([name] or [name]) and be registered as an adverse event.

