5.0 Care escalation procedures in the case of adverse event

- 5.1 If at point of referral or during the course of treatment, Inspire therapists become concerned about the welfare of any participant or immediate family member they will escalate their concerns through Inspire's standardised risk assessment, escalation, management and safeguarding policies and procedures. Where necessary they will contact the participant's GP to mobilise referral to crisis response, NHS primary or secondary care. Likewise, if a safeguarding and vulnerable adults concern is identified this will be escalated, acted on and reported to the relevant statutory body safeguarding team.
 - 5.1.1 The PCL- 5 will be completed at each therapy session. If ≥10 point rise in PCL-5 score occurs since the previous therapy session, or 15-point rise from baseline, or the maximum score of 80 is recorded on the PCL-5, they will use their clinical judgement to assess whether escalation is appropriate.
 - 5.1.2 Any ≥10 point rise in PCL-5 score that occurs since the previous therapy session, or 15-point rise from baseline, or the maximum score of 80 recorded on the PCL-5, will be detected by the unblinded member of the research team (investigator [name]) who will inform the DMEC chair within three working days.
- 5.2 If a participant's PCL-5 score rises by ≥10 points from the previous follow up, or 15point rise from baseline, or the maximum score of 80 is recorded on the PCL5, the unblinded researcher (investigator [name]) will make contact with the participant within six hours of noting the rise in score and encourage them to contact their GP and/or their case worker. They will advise the participant that the researcher will need to contact the participant's case worker (or GP if no case worker) to alert them to the rise in PTSD symptoms.

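### After a qualifying follow-up PCL-5 rise, the researcher's alert need not reach the GP when there is a case worker, although the GP is accountable for safety while therapy is awaited and after discharge

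*Protocol*

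**What the plan says.** Appendix 1 item 5.2 covers follow-up. It is triggered by a PCL-5 rise of at least 10 points from the previous follow-up, a 15-point rise from baseline, or the maximum score of 80. The unblinded researcher contacts the participant within six hours of noting the rise and encourages contact with the GP and/or case worker. The researcher also gives notice of a further step, worded as follows: "contact the participant's case worker (or GP if no case worker) to alert them to the rise in PTSD symptoms".

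Section 14.3 describes the corresponding step for PCL-5 scores that indicate an adverse event. Here the notice given by the researcher reads: "they will need to contact the participants GP and/or case worker to alert them to the rise in PTSD symptoms".

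Accountability is set out separately:

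- Section 14.3: "Before the participant is referred to Inspire and after discharge, the participant's GP holds responsibility and accountability".
- Appendix 1 item 1.3, from discharge to 52 weeks or withdrawal: "the Intervention participant's GP holds responsibility and accountability for the participant's mental health and wellbeing and this includes their safety".
- Appendix 1 item 1.4, for the waiting-list arm: "up until therapy begins the participant's GP continues to hold responsibility and accountability".
- Appendix 1 item 1.2: for the intervention arm, Inspire is accountable from handover of the participant's details until discharge.

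**The concern.** The protocol names one accountable clinician for the periods in which most follow-up scores arrive, and then writes the alert so that this clinician can be missed. The case worker is given no accountability anywhere in the document and the role is not defined. Item 3.1 only lists an Aftercare case worker on the contact card where appropriate. The GP, by contrast, is the route that section 14.3 and item 5.1 name for mobilising crisis response or NHS referral when a therapist is concerned.

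At stake is whether a marked worsening reaches the person the protocol holds responsible. This matters most on the waiting list: people already receiving psychological treatment for PTSD are excluded (section 8.2.2), trial therapy starts only at 20 weeks, and section 8.10.2 relies on Appendix 1 for handling escalating symptoms in that arm.

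**Working it through.** The protocol gives no figure on this point, so the main check is a comparison of texts.

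**Step 1. Whom must the researcher alert?**

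| Situation | Item 5.2 | Section 14.3 |
|---|---|---|
| Case worker exists | Case worker | GP, case worker, or both |
| No case worker | GP | GP |

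In the first row, alerting the case worker alone satisfies both texts. Neither makes a GP alert mandatory. In the second row the GP is always reached, so those participants are unaffected.

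**Step 2. Who is accountable at each follow-up?**

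- Waiting list, 6, 12 and 20 weeks: the GP, because therapy is offered only after the 20-week data are collected (section 8.10.2; item 1.4).
- Intervention arm, 6 weeks: mixed. Therapy starts within three weeks of randomisation (section 10.5) and lasts up to four weeks (section 8.7). The latest planned finish is 3 + 4 = 7 weeks, which is after the six-week follow-up. Anyone still in therapy then is under Inspire (item 1.2).
- Intervention arm, 12, 20 and 52 weeks: the GP, provided therapy keeps to that schedule (item 1.3).

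**Step 3. Does any other text require a GP alert after a follow-up PCL-5 rise?**

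- The opening of Appendix 1 says the intervention's safety will be monitored "through regular contact with the participant's clinical team or GP". This is again an alternative, and it is not tied to a score.
- The self-harm route has a different trigger: "If PHQ9, Q.9 (risk of self-harm) is scored 1-3 this will trigger a safety contact email correspondence from the assessors" (item 2.2.2). The assessor's first contact is "to suggest they may wish to speak to their GP for support" (item 4.2). The GP is contacted only if the participant does not respond to successive messages (items 4.3 to 4.5). A PCL-5 rise with question 9 scored 0 does not enter this route.
- Item 5.1 concerns therapists' worries at referral or during treatment.
- Reports to the principal investigator, the TSC and the DMEC do not inform the GP.

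No other text closes the gap.

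**Step 4. Can the affected group be counted?** A count needs the frequency of a qualifying rise and the share of participants with a case worker.

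The first can be illustrated for one of the three triggers, a rise of 15 or more from baseline, as P = 1 − Φ((15 − mean change)/SD). The inputs are the 52-week feasibility changes in section 5.5, used as a stand-in for other follow-ups:

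- FIRST arm, if it changes like RTM (−15.16, SD 16.00): z = (15 + 15.16)/16.00 = 1.885, P = 3.0%.
- Waiting list, if it changes like TF-CBT (−7.93, SD 13.17): z = (15 + 7.93)/13.17 = 1.741, P = 4.1%.
- Waiting list with an assumed mean change of zero: z = 15/13.17 = 1.139, P = 12.7%; or z = 15/16.00 = 0.938, P = 17.4%.

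The ceiling of 80 makes these figures rather high, and the other two triggers would add to them. The second factor, the case-worker share, appears nowhere in the protocol. The product therefore cannot be formed without inventing an input, and no count is given here.

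**The case against.** The strongest reply is that nothing is broken. A researcher who obeys item 5.2 also obeys section 14.3, so a reader who infers a contradiction goes too far: the appendix is the narrower procedure inside the broader rule. It would also be wrong to infer that the GP is barred from being told or that the rise goes unnoticed. Section 14.3 permits a GP alert. The participant is contacted within six hours of noting the rise and encouraged to seek the GP and/or case worker. A case worker or GP is always alerted. Adverse events go to the principal investigator within 72 hours, to the fortnightly team meeting and into TSC reporting, and safety issues go to the DMEC within 48 hours of that meeting. Every participant is offered a contact card that lists the GP. All of this stands, and it is why the point is minor.

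A second reply is that accountability does not imply notification of every score change, and that GP contact is graded elsewhere. Under the self-harm route, someone who reports such thoughts and replies to the assessor need not be referred to the GP, so a duty to alert the GP about a PCL-5 rise would look stricter. This is fair as far as it goes. But item 5.2 already sends the same rise to the GP for everyone without a case worker, so the protocol itself treats it as worth telling the GP. Having a case worker is not a clear reason to stop.

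A third reply concerns the remedy. A reader might conclude that the GP must be alerted in every case. The documents do not support that, because some intervention participants may still be under Inspire at six weeks. This objection stands, and the fix is worded accordingly.

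**Conclusion.** The point holds as a minor gap in safety routing. When a participant awaiting therapy or already discharged has a case worker, neither item 5.2 nor section 14.3 obliges the researcher to alert the GP, who is the accountable clinician in those periods. Following item 5.2 to the letter leaves the GP out.

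The conclusion rests on the wording alone. It assumes that the case worker holds no accountability stated in pages not shown, and that nothing in the removed consent pages creates a separate duty to inform the GP. The affected group needs both a case worker and a qualifying rise. It is probably small, since most participants are expected to self-refer (section 8.3.2) and case workers are mentioned only where appropriate, but its size cannot be estimated from the protocol. The percentages above describe one trigger and must not be read as numbers of participants missed. The estimand, the analysis and the validity of the efficacy result are not affected.

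**What to change.** Put one identical sentence in item 5.2 and section 14.3. After a qualifying PCL-5 rise, the researcher alerts whoever is accountable at that time: the GP while the participant awaits therapy or after discharge, or Inspire if the participant is still in therapy. The researcher also alerts the case worker where there is one, and tells the participant who will be informed. Before adopting it, check that it agrees with the consent wording on GP contact, which is not shown.

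The change is one sentence in two places and needs no new data field, because GP contact details are already collected at baseline (section 10.1). The price is one extra contact per event for participants with a case worker. Mental-health information would also be disclosed slightly more widely to the GP, in a group whose data section 15.2 treats as particularly sensitive.

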6.0 Care escalation procedures in the case of serious adverse event

- **6.1** A serious Adverse Event that occurs during therapy will be investigated by Inspire according to their standardised clinical protocols and clinical governance framework.
 - 6.1.1 The serious adverse event will be investigated by Inspire's clinical lead or delegated representative using Inspire's standardised SAE procedures template and within an agreed time-frame contingent on the nature and seriousness of the event.
 - 6.1.2 The completed investigation report will include recommendations, shared learning and corrective actions each to be completed within a specified time frame, presented to and signed off by the Inspire CEO Board alongside being shared with the DMEC chair for review.
- **6.2** A Serious Adverse Event that occurs following discharge from Inspire but whilst in the trial will be investigated by one of the study senior investigators (i.e. [name] and [name]) using Inspire's SAE investigational policies and procedures. Inspire protocols and timeframes will be used. The investigational report will be submitted to the DMEC chair.

6.3 The DMEC chair will be notified within 24 hrs of the research team being notified of all serious adverse events.

7.0 Ineligible participants

- 7.1 King's trained and contracted assistant psychologists under supervision from a Consultant Clinical Psychologist (investigator [name]) will determine whether each participant meets the inclusion and exclusion criteria.
- 7.2 During the eligibility confirmation assessment the assistant psychologist will complete a risk assessment, including the PHQ-9, and if the participant discloses suicidal ideation, the assistant psychologist will discuss this with their supervisor and/or a senior member of the research team to decide what action to take.
- 7.3 Those assessed as ineligible for the study will be signposted to alternative specialist voluntary or statutory services. We will provide a safety signposting flyer with contact details for emergency numbers, military organisations and charities that provide support, and offer tailored individual signposting, where appropriate.
- 7.4 For those ineligible, but assessed as high risk, the GP will be contacted to, where necessary, mobilise crisis response and potential referral to NHS primary or secondary care.
- 7.5 Where safeguarding and vulnerable adult's concerns are identified this will be escalated, acted on and reported to the relevant statutory body safeguarding team.
- 7.6 For any individual deemed at immediate high risk and who is unable to keep themselves safe, emergency services will be contacted directly.

